### 11.6.2.2 Elevation of Liver Function Test Parameters

It is strongly recommended that subjects with new ALT or AST elevations of  $\geq 3 \times$  ULN and clinical symptoms be followed closely, including repeat confirmatory testing within 48 to 72 hours of the initial finding, and have subsequent close monitoring of ALT and AST levels, as clinically indicated.

Study drug administration must be interrupted immediately and the Parion medical monitor must be notified if the following criterion is met:

- ALT or AST levels  $>5 \times$  ULN

A thorough investigation of potential causes should be conducted and the subject should be followed closely for clinical progression.

If criteria for study drug interruption is met and no convincing alternative etiology (e.g., acetaminophen use, viral hepatitis, alcohol ingestion) for the elevated ALT or AST levels are identified, regardless of whether the levels have improved, the subject must be discontinued from the study, in consultation with the Parion medical monitor ([Section 9.5](#)). An ETT Visit should be scheduled as soon as possible. Subjects discontinued for elevated ALT or AST levels should be followed until their levels normalize or return to baseline.

If a convincing alternative etiology is identified for the ALT and/or AST elevation, study drug may be resumed when both laboratory values return to baseline or are  $\leq 2 \times$  ULN, whichever is higher, after approval by the Parion medical monitor.

Upon resumption of study drug, ALT and/or AST must be assessed weekly for the shorter of:

- 4 weeks
- 1 week following the last dose of study drug, if ALT and/or AST levels have returned to baseline or  $\leq 2 \times$  ULN

Upon resumption of study drug, ALT and/or ALT levels must be assessed weekly for 4 weeks. If a repeat elevation of  $>5 \times$  ULN occurs within 4 weeks of rechallenge with study drug, then study drug must be discontinued, regardless of the presumed etiology.

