#### 8.1.3.1 Part A

Part A comprises Treatment Period 1, the Washout Period, and Treatment Period 2.

##### 8.1.3.1.1 Treatment Period 1

At the Day 1 Visit, the subject is required to continue to meet all inclusion and exclusion criteria ([Sections 9.1](#) and [9.2](#)) and continue to have stable PCD disease, in the opinion of the investigator. The first dose of inhaled study drug will be administered after randomization on Treatment Period 1 Day 1. Inhaled study drug should be taken according to instructions provided within the protocol. Study clinic visits will occur on Day 1 and Day 29 to allow for a full 28 days of treatment.

If the first dose of inhaled study drug administered in the clinic on Day 1 is taken in the morning, the second dose will be taken that evening. The last dose of the twice daily study regimen will be taken on the evening of Day 28 and no dose will be taken before the morning visit on Day 29.

If the first dose of inhaled study drug on Day 1 is taken in the clinic in the afternoon, a second dose will not be taken that evening. The last dose of the twice daily study regimen in Treatment Period 1 will be taken on the morning of Day 29, at least 4 hours before the Day 29 Visit.

Subjects should only take the inhaled study drug at a maximum of twice daily.

At Day 4 ( $\pm 1$  day), subjects will have a telephone call from the study coordinator or authorized site designee for safety purposes to ascertain if there have been any AEs. If necessary to follow up on a new medical problem, the subject may be asked to return to clinic.

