**A subject will be withdrawn from study drug for any of the following reasons:**

- Parion Sciences, regulatory authorities, or the site's institutional review board (IRB) or independent ethics committee (IEC) close the study.
- A female subject or a female partner of a male subject has a confirmed pregnancy.
- A subject has persistent and severe bronchospasm related to study drug administration.
- A subject's treatment is unblinded by the investigator.
- Development of a life-threatening AE or a serious adverse event (SAE) that places him/her at immediate risk, and discontinuation of study drug deemed necessary.

**A subject may be withdrawn from study drug after a discussion between the investigator and the Parion medical monitor for any of the following reasons:**

- Development of a medical condition that requires prolonged concomitant therapy with a prohibited medication or prolonged interruption of the study drug.
- Noncompliance with study requirements.
- A serum potassium level  $>1.1 \times \text{ULN}$ , confirmed by a plasma potassium level  $>1.1 \times \text{ULN}$ . A confirmatory serum and plasma potassium level may be drawn at the discretion of the investigator before making the decision to remove a subject from the study. Refer to [Section 11.6.2.1](#) for further guidance on treatment of hyperkalemia.
- The subject has a relative decline in  $\text{ppFEV}_1$  of  $\geq 15\%$  from their Day 1, Day 57, or Day 85 Visit pre-dose value.
- An increase in ALT or AST according to evaluations and management described in [Section 11.6.2.2](#).

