#### **11.6.2.1 Hyperkalemia**

The standard of care for management of hyperkalemia should be applied. A thorough investigation of potential causes should be conducted, and the subject's potassium level should be followed closely.

If hyperkalemia occurs, study drug should be interrupted until the serum and plasma potassium are in the normal range. If no convincing temporary or possibly reversible alternative etiology (e.g., oral intake of potassium, acute renal failure, metabolic acidosis, uncontrolled diabetes mellitus, admission of repeated fist-clenching during phlebotomy, hemolyzed sample) for the elevated potassium is identified, study drug treatment must be discontinued regardless of whether the level has improved; this decision should be made in consultation with the Parion medical monitor or authorized designee. Subjects in whom treatment is discontinued for elevated potassium should have their potassium levels monitored closely until levels normalize or return to baseline.

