5.5 IMPORTANT PROTOCOL DEVIATIONS

An important protocol deviation (IPD) is a deviation that may significantly affect the completeness, accuracy, or reliability of the study data or that may significantly affect a subject's rights, safety, or well-being. IPD rules will be developed and finalized prior to the database lock.

The protocol deviations that should be considered as potential IPDs include, but are not limited to:

[figure not shown]
- Subject was randomized despite the violation of inclusion/exclusion criteria
- Subject was less than 80% compliant with study drug
- Subject received prohibited concomitant medications
- Subject received the wrong treatment or incorrect doses
- Subject remained in the study despite meeting withdrawal criteria

Occurrence of any of these events should be considered as potential IPDs, but a blinded team should categorize them as IPDs only if they have the potential to significantly affect the completeness, accuracy, or reliability of the study data or that may significantly affect a subject's rights, safety, or well-being.

IPDs (from the clinical database or from the site deviation log) will be summarized descriptively based on the FAS and presented by treatment sequence in Part A and by treatment in Part B. Additionally, IPDs will be provided in an individual subject data listing.

1006696
Parion Sciences Incorporated
CLEAN-PCD
SAP Version 1.0

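### Protocol 11.6.2.2 gives two durations for ALT/AST testing after rechallenge, and 9.5 and 11.6.2.1 differ on whether, and at what value, raised potassium ends treatment

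*Protocol*

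**What the plan says.** **Testing after resumption.** Protocol 11.6.2.2 gives two consecutive instructions. The first reads "Upon resumption of study drug, ALT and/or AST must be assessed weekly for the shorter of" and lists two limits: 4 weeks, or "1 week following the last dose of study drug, if ALT and/or AST levels have returned to baseline or" at most 2 x ULN. The second reads "Upon resumption of study drug, ALT and/or ALT levels must be assessed weekly for 4 weeks". It offers no shorter option and names ALT twice. The next sentence ends study drug, whatever the cause, if a value above 5 x ULN recurs within 4 weeks of rechallenge.

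**Stopping rules.** Protocol 9.5 has a mandatory list and a discretionary one, which opens "A subject may be withdrawn from study drug after a discussion between the investigator and the Parion medical monitor". Potassium and ALT/AST are only on the discretionary list. The potassium item has its own trigger, a serum value above 1.1 x ULN confirmed by plasma above 1.1 x ULN, and refers to 11.6.2.1 for treatment guidance. The ALT/AST item has no trigger and points to 11.6.2.2.

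Protocol 11.6.2.1 interrupts drug when hyperkalemia occurs. If no convincing temporary or reversible cause is found, "study drug treatment must be discontinued regardless of whether the level has improved", in consultation with the medical monitor. It gives no potassium value. Protocol 11.6.2.2 says of ALT or AST above 5 x ULN with no convincing alternative cause that "the subject must be discontinued from the study, in consultation with the Parion medical monitor". Protocol 9.5 says subjects taken off study drug continue to be followed unless they withdraw consent.

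**SAP.** Section 5.5 lists as a potential important protocol deviation: "Subject remained in the study despite meeting withdrawal criteria".

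**The concern.** Two sites could treat the same subject differently and each point to protocol text in support. After a liver rechallenge, one could stop weekly testing a week after the last dose while another continued to 4 weeks. For confirmed raised potassium with no other explanation, one could treat withdrawal as a matter for discussion and another as required. Potassium is a watched risk here: it is measured in both serum and plasma, and a value above ULN excludes at screening. What is at stake is consistent handling of subjects and comparable safety data. A further, smaller matter is what the SAP's deviation item on withdrawal criteria would be checked against.

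**Working it through.** There is no planned figure to reproduce. One day-count and one side-by-side reading are enough.

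**1. When the two testing rules differ**

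Inputs: r is the study day of resumption and L the study day of the last dose. L is Day 28 for a subject who takes no drug after Period 1 (Protocol 8.1.3.1.1, morning start: "The last dose of the twice daily study regimen will be taken on the evening of Day 28"), Day 84 if dosing ends with Period 2, and Day 112 if it ends with Part B (8.1.3.1.3 and 8.1.3.2.1).

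- First rule, levels recovered: min(28, L + 7 − r) days. If levels have not recovered, 28 days.
- Second rule: 28 days.
- They differ when L + 7 − r < 28, that is, when L − r < 21. The gap is then 21 − (L − r) days, from 1 day (L − r = 20) to 21 days (L = r).

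| Last dose L | Rules differ from resumption on | Example r | First rule | Second rule |
|---|---|---|---|---|
| Day 28 | Day 8 | Day 16 | 28 + 7 − 16 = 19 | 28 |
| Day 84 | Day 64 | Day 72 | 84 + 7 − 72 = 19 | 28 |
| Day 112 | Day 92 | Day 100 | 112 + 7 − 100 = 19 | 28 |
| Day 112 | Day 92 | Day 88 | min(28, 31) = 28 | 28 |
| Day 84 | Day 64 | Day 16 | min(28, 75) = 28 | 28 |

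With an afternoon start the last dose moves to Day 29, 85 or 113, and each boundary moves one day later.

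The recovery condition will usually be met, because 11.6.2.2 lets drug resume only once levels are back to baseline or at most 2 x ULN, whichever is higher.

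**2. The repeat-elevation window**

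The window closes on day r + 28. For r = 100 and L = 112, required testing under the first rule can end on Day 119 (112 + 7), while the window runs to Day 128 (100 + 28). That leaves 9 days with no required test.

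**3. Potassium, no alternative cause found**

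| Finding | Protocol 9.5 | Protocol 11.6.2.1 |
|---|---|---|
| Serum above 1.1 x ULN, confirmed in plasma | May be withdrawn, after discussion | Must be discontinued |
| Above ULN, up to 1.1 x ULN | Not listed | Depends on what hyperkalemia means; no value given |

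The first row is a direct difference in status. The second is an undefined trigger. The SAP does not settle it: Appendix III starts its hyperkalemia categories at values above ULN, while SAP 10.2 separately summarizes values above 1.1 x ULN.

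**4. Study or study drug**

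Protocol 9.5 concerns withdrawal from study drug with continued follow-up. Protocol 11.6.2.2 says discontinued from the study, yet also asks for an early termination visit and follow-up until levels normalize.

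**The case against.** Several points on the other side are sound.

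- **Last dose.** A reader might infer that the rules conflict after the first week of every period. The documents do not support that. Protocol 8.1.4 uses the unqualified phrase for the end of dosing in the study, and 12.3.1 names the period when it means a period. A subject who resumes in Period 1 and goes on to Day 84 gets 28 days under both rules.
- **Reach.** The first scheduled on-treatment chemistry is Day 15, and only if that visit is held; otherwise it is Day 29. Early resumption within a period would need an unscheduled draw or a late-reported pre-dose result. Weekly testing for 4 weeks also meets the first rule if that rule is read as a minimum.
- **The window.** Where the rules differ on this reading, dosing ends before the window does, and testing covers the dosing days. What can be missed is a late repeat rise, not a stop during dosing.
- **ALT/AST may or must.** A reader might infer the same status conflict for liver tests. The 9.5 item adopts the management in 11.6.2.2, which largely settles it.
- **Potassium between ULN and 1.1 x ULN.** A reader might infer a contradiction because one section interrupts drug where the other does nothing. Interrupting at a lower level than withdrawing is not contradictory. What survives is that the mandatory discontinuation clause has no value.
- **Safeguards.** The potassium and ALT/AST stopping decisions involve the medical monitor, which limits divergence between sites.
- **Part B.** A reader might infer that ivacaftor brings its own liver rules. Protocol 11.6.2.2 covers study drug generally and has none specific to it.

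These points reduce how often the conflicts arise. They do not remove the two unlinked testing sentences or the potassium mismatch.

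**Conclusion.** The point holds within these limits. Protocol 11.6.2.2 contains two testing durations that cannot both be the intended rule. They differ by 1 to 21 days when the last dose falls less than 21 days after resumption, assuming recovered levels and reading last dose as the last dose in the study. Under the first rule, required testing can end before the repeat-elevation window closes. On potassium, 9.5 and 11.6.2.1 differ both in status (discretionary against mandatory) and in trigger (a confirmed value against an undefined term). The study versus study-drug wording in 11.6.2.2 is a lesser point, with no differing assessment shown.

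The number of subjects affected cannot be derived from the documents and is probably small. A reader might infer that the SAP's deviation analysis is compromised. It is not: SAP 5.5 lists only potential deviations, leaves the rules to be finalized before database lock, and has a blinded team classify them; no analysis set depends on them. No planned statistical figure changes.

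**What to change.** - In Protocol 11.6.2.2, reconcile the two testing sentences into one duration, make that duration and the repeat-elevation window consistent with each other, state whether last dose means in the period or in the study, and correct the repeated ALT.
- Reconcile 9.5 and 11.6.2.1 on the potassium trigger and on whether stopping is discretionary or mandatory.
- Align study and study drug between 11.6.2.2 and 9.5.
- Have the important-deviation rules under SAP 5.5 refer to the reconciled criteria when they are finalized.

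Which rule is right in each case is for the sponsor's clinicians. The cost is protocol wording in three sections and one reference in the deviation rules. No analysis, sample size or dataset changes.

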### 11.6.3 Physical Examinations and Vital Signs

A complete physical examination will be performed at the Screening Visit, Day 1, Day 29, Day 57, Day 85, Day 113, and ETT visits. At the Day 15, Day 71 and Day 99 visits (if completed), an abbreviated physical examination will be done. The complete physical examination will include the following components: HEENT (head, eyes, ears, nose, and throat), neck, chest and chest auscultation, cardiovascular, abdomen, skin, and musculoskeletal. The abbreviated physical examination will include the following components: HEENT, neck, chest auscultation, cardiovascular, and skin. Both the full and abbreviated physical examinations will exclude rectal and genitourinary examinations (see [Table 3-1](#), [Table 3-2](#), and [Table 3-3](#)).

After the Screening Visit, any clinically significant abnormal findings in physical examinations will be reported as AEs.

Vital signs include blood pressure (systolic and diastolic), body temperature, pulse rate (beats per minute), respiratory rate (breaths per minute), and pulse oximetry. These will be assessed

following at least a 5-minute rest in a sitting or supine position. After the Screening Visit, clinically significant abnormal findings in vital signs will be reported as AEs.

#### **11.6.4 Electrocardiograms**

Twelve-lead ECGs will be performed using a machine with printout according to the Schedule of Assessments (Table 3-1, Table 3-2, and Table 3-3). Additional 12-lead ECGs will be performed at any other time if clinically indicated. The performance of all ECGs will adhere to the following guidelines:

- The subject will be instructed to rest in a sitting or supine position for at least 5 minutes before having an ECG performed.
- Prior to placing ECG leads, the record will be reviewed for the presence of dextrocardia. Subjects with dextrocardia will have all ECG limb and chest (V) leads reversed.

The ECG traces will be manually read at the study site at the Screening Visit, Day 1, Day 15 (if a visit is conducted), Day 29, Day 57, Day 71 (if a visit is conducted), Day 85, Day 99 (if a visit is conducted), Day 113, and the ETT Visit. A printout of the ECG traces will be made for safety review by the investigator and maintained with source documentation. Clinically significant ECG abnormalities (taking into consideration anticipated abnormalities in subjects with dextrocardia) occurring during the study through the Day 113 Visit will be recorded as AEs.

To ensure safety of the subjects, a qualified individual at the study site will make comparisons to baseline measurements. If the QTcF increases by  $>45$  msec from the baseline or an absolute QTcF value is  $\geq 500$  msec for any scheduled ECG, 2 additional ECGs will be performed approximately 2 to 4 minutes apart to confirm the original measurement. If the QTcF value remains above the threshold value on the repeat ECG measurement with no identified alternative etiology for the increased QTcF, then study drug should not be administered on that day and must be immediately interrupted. An ECG should be repeated within 48 to 72 hours to monitor the QTcF interval. Discussion with the Parion medical monitor must occur to determine whether study drug may be resumed or whether discontinuation from study drug treatment is indicated.

Subjects in whom treatment is discontinued for increased QTcF should have their QTcF monitored closely until it normalizes or returns to baseline.

#### **11.6.5 Contraception and Pregnancy**

The effects of VX-371 on conception, pregnancy, and lactation of humans are not known.

Ivacaftor did not show any effect in reproductive toxicology studies, including rat fertility, rat and rabbit embryo-fetal development, and rat peri/post-natal reproduction toxicity studies (refer to the Ivacaftor Investigator's Brochure).

Results suggested that the clinical effects of the oral contraceptive would not likely be adversely impacted by coadministration with ivacaftor. Therefore, hormonal contraceptives are one acceptable means of contraception for female subjects of childbearing potential in this study.

##### **11.6.5.1 Contraception**

Participation in this study requires a commitment from the subject and his/her partner to use at least 1 acceptable method of contraception, which must be used correctly with every act of

sexual intercourse. Methods of contraception should be in successful use from at least 14 days before the first dose of study drug (unless otherwise noted) and until 90 days following the last dose of study drug.

**Contraception for the couple is waived for the following:**

- True abstinence for the subject, when this is in line with the preferred and usual lifestyle of the subject. Periodic abstinence (e.g., calendar, ovulation, symptothermal, post-ovulation methods) and withdrawal are not acceptable methods of contraception.
- If the male is infertile (e.g., bilateral orchiectomy). Infertility may be documented through examination of a semen specimen or by demonstration of the absence of the vas deferens by ultrasound before the first dose of the study drug.
- If the female is of non-childbearing potential, per the following:
  - Documented hysterectomy or a bilateral oophorectomy/salpingo-oophorectomy.
  - Postmenopausal: continuous amenorrhea for at least 12 months and serum FSH levels  $\geq 40$  mIU/mL.
  - Has not achieved menarche (has not had her first menstrual period). If a female achieves menarche during the study, she will need to follow acceptable methods of contraception or abstinence.

**For subjects for whom contraception methods are not waived due to one of the reasons cited above, the following are acceptable contraceptive methods for male subjects and their female (non-study) partners, and for female subjects and their male (non-study) partners:**

**Table 11-2 Acceptable Methods of Contraception**

- 
- Male vasectomy 6 months or more previously, with a negative post-vasectomy semen analysis for sperm.
  - Male or female condom with or without spermicide (either as a single product if commercially available and/or allowed according to local regulations; otherwise condom and spermicide as separate products).
  - Female bilateral tubal ligation performed at least 6 months previously.
  - Female diaphragm, cervical cap, or vaginal sponge, each with spermicide (where available).
  - Female continuous use of an intrauterine device (non-hormone releasing or hormone releasing) for at least 90 days.
  - Female combined (estrogen and progestogen-containing) or progestogen-only hormonal contraception associated with inhibition of ovulation if successfully used for at least 60 days.
- 

**Important notes:**

- Local requirements may prohibit the use of some of these acceptable methods listed above. Please contact the Parion medical monitor with any questions.
- If applicable, additional contraception requirements may need to be followed according to local regulations and/or requirements.
- Male and female subjects who are not sexually active at the time of screening must agree to follow the contraceptive requirements of this study if they become sexually active.

- Female condom used with male condom (as a double method of contraception) is not an acceptable method of contraception due to risk of tearing; a different acceptable method of birth control must be used as described in [Table 11-2](#).
- Male subjects must not donate sperm after the first dose of study drug, throughout the study, and for 90 days following the last dose of study drug.
- Female subjects and female partners of male subjects should not plan to become pregnant during the study through 90 days following the last dose of study drug.
- Female subjects should not nurse a child from the start of study drug dosing through 90 days following the last dose of study drug.

Unique situations that may not fall within the above specifications may be discussed with the Parion medical monitor on an individual basis.

